Based on our work and others, we project that 47-58% ( $n =56-70$ ) will worsen in frailty status over the period of the study ([name] et al., 2012; Gill et al., 2006). This is likely an under-estimate given the fact that all subjects in this study will be pre-diabetic and will be at increased risk for developing diabetes as compared to this prior work.

Aim 2. The goal of this Aim is to gain insight into the mechanism(s) underlying the effect of metformin on frailty. In Aim 2 we will test two potential mechanisms:

(1) A reduction in insulin resistance (i.e., increased insulin sensitivity). Because metformin is an insulin sensitizer used to treat type-2 diabetes, metformin could reduce/delay the development of frailty through its action on the natural course of diabetes development.

(2) A reduction in chronic inflammation. As noted above, increased inflammation is believed to be fundamental in the etiology of frailty. Because metformin has been reported to reduce inflammation in subjects with diabetes (Carter et al., 2005), metformin could reduce/delay the development of frailty by reducing the inflammation in pre-diabetic subjects.

To test these two potential mechanisms we will measure:

- 1) insulin sensitivity at baseline, at year 1, and year 2 (at the end of the study). However, if a participant converts to diabetes based on the oral glucose tolerance test which will be conducted every 6 months, insulin sensitivity will be measured immediately without waiting until the 1 or 2 year time point
- 2) markers of tissue inflammation (muscle) at baseline, year 1, and year 2 (end of the study)
- 3) markers of systemic inflammation (plasma) at baseline and every 6 months thereafter during the two years of treatment with metformin (or placebo)

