#### Experimental

#### **Screening Tests**

a) Telephone Screening Potential participants will be asked screening questions over the phone. Only those without exclusion criteria will be scheduled for an in-person screening visit.

b) History & physical examination will be performed by [name] (board-certified Internist and Geriatrician) to document medical history and physical exam findings according to key inclusion/exclusion criteria (see Human Subjects). The history & physical examination will also include screening questions for cognition, quality of life, and depression. Human studies will be conducted in the Bartter Research Unit (BRU) of the ALMVAH and at the MARC on the 3rd Floor; however, the Visits 2, 8 and 14 which include the Insulin Clamp and Muscle Biopsy will continue to be done at the ALMVAH BRU. Waist circumference using the World Health Organization protocol will also be measured as part of the history & physical examination.

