c) Frailty assessment: Individuals identified as frail (approximately 10% of the community-dwelling older adult population) ([name] and Hazuda, 2008) will be excluded. Pre-frailty is defined as the presence of 1 or 2 of: 1) self-reported unintentional weight loss of 10 lbs or more in last year, 2) self-reported exhaustion, 3) low physical activity based on the Minnesota Leisure Time Physical Activity Questionnaire, 4) weak hand grip, 5) and slowness on 10-foot walk at usual pace. These measures have been standardized in SALSA, and will be used in this study as described ([name] and Hazuda, 2008). Non-frailty is defined as the presence of 0 characteristics. Frailty will be assessed every 6 months using the Fried criteria. If a participant's frailty category or score worsens based on Fried criteria (Fried et al., 2001), it will be repeated in 3 months and then at the 6 months intervals as per the protocol thereafter. At the baseline, self-reported unintentional weight loss will be used as criteria for weight loss as stated above. However, at all subsequent visits, individuals who have lost  $\geq 5\%$  of their baseline weight will be considered to have met the criteria for weight loss. As a measure of lower extremity function, we will use the Short Physical Performance Battery (SPPB) (Guralnik et al., 1994) and the 6-Minute Walk Test (6-MWT) (Harada et al., 1999). Both the SPPB and the 6-MWT are assessments of physical function commonly used in geriatrics studies. Lower extremity strength will be measured every 6 months with a knee extension dynamometer chair. The participants will be positioned in an upright position, with the ankle to a force or torque transducer at the knee angle of  $90^\circ$ . After 3 warm-up trials, 3 trials will be conducted to measure maximal voluntary contraction force of the knee extension muscle. We will also screen for depression using the Geriatric Depression Scale (Yesavage et al., 1982) and cognitive

impairment using the Mini Mental State Examination (Folstein et al., 1975) as part of the frailty assessment.

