k) Management of conversions: Any one of the following will prompt 2-hour OGTT to confirm possible diagnosis of diabetes: fasting glucose  $\geq$  126 mg/dL, HbA1c  $\geq$  6.5%, 2-hour OGTT glucose of  $\geq$  200 mg/dL, or clinical signs and symptoms of diabetes. If any of these occur, OGTT will be conducted within 6 weeks. If the subsequent 2-hour OGTT glucose is  $\geq$  200 mg/dL, diabetes conversion will be confirmed. If diabetes conversion occurs based on the OGTT, measurements of frailty, insulin sensitivity (clamp), body composition (DEXA), coagulation tests, stool sample, and inflammation (muscle and systemic) will be

performed. If these assessments are conducted within 1 month of the 12 month or 24 month assessments, the 12 or 24 month assessments will not be conducted. After these repeat measurements are performed, the study allocation will be unblinded, and, if receiving placebo, subjects will be initiated on metformin and titrated as above. Medication management will occur by an independent practitioner (MD or NP) on the study staff who is not the PI such that the PI will remain blinded to study treatment. Hemoglobin A1c will be monitored in those who have converted to diabetes, and, if it reaches  $\geq 7.5$ , subjects will be initiated on 15 mg pioglitazone in addition to metformin unless there is a contraindication to pioglitazone. The rationale for adding pioglitazone versus other antidiabetic agents is that the low dose metformin-thiazolidinedione combination has been shown to have a potent effect to prevent diabetes (Zinman et al., 2010). Pioglitazone will be increased to 30 mg if hemoglobin A1C remains  $\geq 7.5$ . Pioglitazone will not be initiated in any subject with the following: hematuria, history of bladder cancer, lower extremity edema  $> 1+$ , or known history of osteopenia or osteoporosis. Subjects will be seen every 3 months for monitoring of HbA1C. If maximal metformin (1000 mg BID) and pioglitazone (30 mg daily) doses are reached (or if the patient cannot tolerate metformin and/or pioglitazone) and HbA1C remains  $\geq 8$ , subjects will be referred to their primary care physicians for further treatment, but will remain in the study for frailty assessment and all other follow-up studies. Subjects who initially were on metformin will receive pioglitazone 15 mg (in addition to metformin) if Hemoglobin A1c reaches  $\geq 7.5$ , which will be titrated to 30 mg if necessary as described above.

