**Follow up visits.** History/physical exam will be conducted every 6 months. Fasting glucose measurement and HbA1c will be conducted every three months, and OGTT will be conducted every 6 months. However, if fasting glucose and/or the HbA1c suggest conversion to diabetes based on American Diabetes Association criteria, OGTT will be performed. Assays of systemic inflammation (in plasma) will be conducted every 6 months. Insulin clamp with muscle biopsies will be conducted at 12 and 24 months, such that the treatment effect on tissue inflammation and insulin signaling may be determined. The table below outlines the follow up visits and procedures. A grace period of +/- 3 weeks is provided to complete follow-up visits.

Study visits and procedures															
Visit #	1	2	3	4	5	***6	7	8	9	***10	11	***12	13	14	15
Year	1												2		
Month	Screening Visit	0	1	3	6	9	12	12	12	15	18	21	24	24	24
Time Interval		3-21* Days	5-7 Days	2.5 Mo	3 Mo	3 Mo	3 Mo	3-21 Days	5-7 Days	2.5 Mo	3 Mo	3 Mo	3 Mo	3-21 Days	5-7 Days
History & Physical, with Frailty Assessment	X			X	X		X				X		X		
Biodex	*X				*X		*X			*X			*X		
Activity monitor		X							X						X
Quality of life assessment	X			X	X		X				X		X		
EKG	X						X								X
Urinalysis	X						X								X
OGTT	X				X		X				X		X		
Safety labs	X			X	X	X	X			X	X	X	X		
HbA1c	X			X	X	X	X			X	X	X	X		
Coagulation tests	X						X								X
Systemic inflammation		*X			X			*X			X				*X
DEXA		*X							*X						*X
Stool collection		*X							*X						*X
Insulin clamp w/ biopsy		*X							*X						*X
Examination of biopsy site			**X							**X					**X

\*These visits may be done at other approximate visits to reduce the amount of exposure to the participant due to COVID-19.

\*\*Due to COVID-19, the participants can opt to do this visit via phone or in person.

\*\*\*Due to COVID-19, if the participants do not need to do the Frailty assessment, this visit can be done via phone. Labs may be performed at the Quest Diagnostics laboratory nearest to the participant instead of the research unit.

**Urinalysis (UA) will be repeated if needed prior to starting on pioglitazone (only for subjects who convert to diabetes and do not have adequate glycemic control on metformin alone).**

**Basic metabolic panel (kidney function) will be performed as needed to check kidney function at least 48 hours after any radiologic exam using contrast dye.**

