**DEXA may be performed at Visit 7 instead of Visit 8 and at Visit 13 instead of Visit 14 if participant unable to arrive early to the clinical research unit on Visit 8 and Visit 14.**

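### Section k) lets a conversion set replace a nearby 12- or 24-month set but not the reverse, so a conversion confirmed just after the clamp visit is by default sent for a second clamp and biopsy within weeks

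*Combined protocol and SAP*

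**What the plan says.** Item 6, Study Procedures k) sets the sequence. A raised fasting glucose, HbA1c or 2-hour OGTT value, or clinical signs and symptoms, prompts a confirmatory test: "If any of these occur, OGTT will be conducted within 6 weeks". If that test is positive, the participant has frailty, clamp, DEXA, coagulation, stool, and muscle and systemic inflammation measurements. If this conversion set is done "within 1 month of the 12 month or 24 month assessments, the 12 or 24 month assessments will not be conducted". The section then continues: "After these repeat measurements are performed, the study allocation will be unblinded", and participants found to be on placebo start metformin.

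The Aim 2 text under Research Design and Methods gives the purpose of the early clamp. On conversion, "insulin sensitivity will be measured immediately without waiting until the 1 or 2 year time point".

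Screening Tests b) places the invasive procedures at "Visits 2, 8 and 14 which include the Insulin Clamp and Muscle Biopsy". In the visit table, the scheduled OGTT, HbA1c and frailty assessment are at Visits 7 and 13, and Visits 8 and 14 follow 3-21 days later. The text above the table adds: "A grace period of +/- 3 weeks is provided to complete follow-up visits". A note below it says: "DEXA may be performed at Visit 7 instead of Visit 8 and at Visit 13 instead of Visit 14", for participants who cannot arrive early.

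**The concern.** The waiver was written for a conversion that comes before the annual set. The opposite order can also occur. The OGTT at Visit 7 or 13 raises the flag, the clamp and biopsy visit goes ahead as scheduled, and the confirmatory OGTT comes back positive afterwards. Symptoms that arise around or shortly after the clamp visit lead to the same place. By then there is no scheduled set left to cancel, and section k) still orders the conversion set.

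What is at stake is burden with little scientific return, in people aged 65 or older. The protocol's own risk section lists local hematoma in fewer than 2% of biopsied subjects and transient numbness or altered sensation in about 1 in 50. The two sets would be taken while the participant is still blinded, with no change of treatment ordered between them. Because unblinding follows the repeat, a placebo participant with confirmed diabetes also waits for it before starting metformin.

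**Working it through.** The plan states no figure on this point, so there is nothing to reproduce. The check is date arithmetic from the stated windows.

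**Inputs.** Day 0 is Visit 7 or 13, when the flag is raised.
- Clamp day v: 3 to 21 (visit table), or 3 to 42 if the whole +3-week grace is used (21 + 21).
- Confirmatory OGTT day c: 1 to L. L = 42 is the 6-week limit in section k). L = 21 and L = 14 are assumed faster practices.
- Scheduled clamp days: 3 (Visits 2, 8, 14), with 2 biopsies each (Study Procedures d; Potential risks 4).

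**Largest gap.** Gap = c - v. With confirmation on day 42:
- clamp on day 3: 42 - 3 = 39 days
- clamp on day 12: 42 - 12 = 30 days
- clamp on day 21: 42 - 21 = 21 days

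**How often the order is reversed.** The documents give no distribution of dates, so I assume that all permitted day pairs are equally likely. The share is the number of pairs with c > v divided by (number of v values) x L.

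| Limit L | No grace (19 values of v) | Full +3-week grace (40 values of v) |
|---|---|---|
| 42 days | 570/798 = 71.4% | 780/1680 = 46.4% |
| 21 days | 171/399 = 42.9% | 171/840 = 20.4% |
| 14 days | 66/266 = 24.8% | 66/560 = 11.8% |

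For example, at L = 42 without grace the numerator is 39 + 38 + ... + 21 = 570.

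**Would a plain 1-month reciprocal window be enough?** Gaps over 30 days arise only for clamp days 3 to 11: 9 + 8 + ... + 1 = 45 pairs. That is 45/570 = 7.9% of the reversed pairs without grace and 45/780 = 5.8% with it. A 30-day window alone would miss these.

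**Would a rule tied only to the flag be enough?** No. Take symptoms 5 days after Visit 8 and confirmation 7 days later. The clamp is then 5 + 7 = 12 days old, but it came before the flag, so a flag-only rule would still order the repeat. Both conditions are needed.

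**Burden per affected participant.** Clamps rise from 3 to 4. Biopsies rise from 3 x 2 = 6 to 7 or 8. The lower count follows from section k) naming muscle inflammation but not insulin signaling: Study Procedures d) takes inflammation from the pre-clamp biopsy and insulin receptor signaling from the second. The higher count follows from Potential risks 4, which says the biopsy is done twice on any biopsy day.

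**The case against.** The best defence is that the intent is plain. The 1-month window in section k) is not limited to the time before the annual visit, and its purpose is evidently one set rather than two. The Aim 2 sentence explains the early clamp as a way not to wait for the annual one, and that reason disappears once the annual clamp is done. This shows that a repeat serves little purpose. It does not change the text: on either side of the window, the only stated consequence is that the 12- or 24-month set is dropped.

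The default is also soft. The investigator may omit a clamp, biopsy or DEXA on various grounds. Blood loss is capped at 600 ml in two months, although the volume drawn on a clamp day is not given. A site may confirm before the clamp visit, or use the grace to delay that visit. All of this stands, and many repeats may be avoided in practice. But these are case-by-case exits. None is a rule for this situation, so similar participants could be handled differently.

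The month-24 case is weaker, because Visit 14 comes at the end of the two-year study. No text switches section k) off there, but month 12 is the case that matters.

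A reader might infer three stronger things that the documents do not support. One is that two further biopsies are certain: section k) can be read to need only one. Another is that 46% or 71% of converters would be affected: these are shares of calendar combinations under an assumed uniform spread, and sites choose both dates. The third is that the trial's inference is compromised: nothing here touches the primary analysis, the significance level or the power.

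**Conclusion.** The point holds as a gap in the procedures that affects participant burden. By its wording, section k) sends a participant whose conversion is confirmed after Visit 8, or less importantly Visit 14, for a near-duplicate set: one clamp with tritiated glucose, one or two biopsies and possibly a DEXA. For a flag at Visit 7 or 13, confirmation comes at most 39 days after the clamp. Unblinding and any metformin start come after the repeat.

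The sequence rests on the stated windows alone. The shares of 12% to 71% rest on equally likely dates and, below the 6-week limit, on assumed confirmation times. How many participants would be affected cannot be worked out, because the documents do not say how many conversions would be flagged near these visits. The change is worth making because it is cheap and because the protocol already accepts one set in place of another within a month. It is not a condition for the validity of the trial.

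**What to change.** Make the waiver in section k) reciprocal, for example: *If the 12- or 24-month set was completed after the flag, or within 1 month before conversion is confirmed, it serves as the conversion set and is not repeated; any item not obtained can still be done. Where possible the confirmatory OGTT is done before Visit 8 or 14.* It should be clear that the set includes the frailty assessment from Visit 7 or 13.

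The cost is two sentences and no added visits. Each affected participant is spared up to one clamp, two biopsies and possibly one DEXA, and unblinding no longer waits for them. The price is that conversion measurements may predate confirmation. For a flag at Visit 7 or 13 this is by up to 42 - 3 = 39 days for the clamp and biopsy and up to 42 days for frailty. A symptom flag on another date shifts these limits. Where the frailty assessment is then older than the sponsor wants, it can be exempted from the waiver and repeated without any invasive procedure.

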#### Data Analysis Plan:

### STATISTICAL METHODS & POWER CALCULATIONS

**Overview.** In all analyses for Aim 1 and Aim 2, primary inference will be drawn based on intention to treat (ITT) analyses. Average complier effect (ACE) will be used to inform the metformin effect under full compliance to treatment assignments (Angrist et al, 1996). Per protocol analyses will be used to inform the metformin effect among completers. All analyses will be carried out unadjusted and with adjustment for covariates (Table 7) and covariate interactions with treatment and time. Corrections for multiple comparisons will be applied as appropriate.

The impact of metformin treatment on the progression of frailty status (non-frail, pre-frail, frail) over time will be assessed with a repeated measures mixed effects multinomial logistic model that models the log-odds of adjacent frailty statuses in terms of an indicator of metformin use, time, and the metformin use by time interaction. The possibility of non-linear trends of the log-odds of frailty statuses will be assessed by including an additional time factor (e.g., time squared) and its interaction with metformin use. The best fitting model will be used for inference. Secondary outcomes including gait speed, 6 minute walk, SPPB, frailty index constructed from the research data collected according to the Rockwood index (Searle et al., 2008; Rockwood et al., 2007), and body composition will similarly assessed. Under the linear trend model, the beneficial impact of metformin will be revealed by a significant time by treatment interaction associated with the log-odds of frailty status progression, indicating that the rate of increase in the likelihood of frailty progression over time is reduced in the metformin arm relative to the placebo arm. Under the non-linear trend model, the impact of metformin will be revealed by a significant reduction in the log-odds of frailty status progression in the metformin arm versus placebo at certain time points during the follow-up. SAS proc **nlmixed** will be used in the mixed effects model analyses. Proc **nlmixed** is preferred over other mixed effects modeling procedures such as GEE because it is valid under missing at random (MAR) assumption, accommodates linear and non-linear modelling, and uses maximum likelihood estimation.

Table 7. Covariates included in statistical analyses

Categories of covariates	Baseline	Time Varying
Demographics (age, sex)	X	
BMI (obesity), sarcopenia	X	X

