**3.D.3. Power Calculation for Aim 1.** With 60 completers per arm, this study will achieve a power of 86% to detect an overall odds ratio of 0.20 for a one ordinal category increase in the frailty score in metformin versus placebo based on SAS **proc nlmixed** analyses of 1000 simulated databases with 6 repeated measures per subject, all subjects at frailty score 0 or 1 at baseline, an increasing random pattern in the placebo group, a pattern of lower frailty scores with increasing time on study in the treated group, and 10% of subjects in each arm remaining at baseline levels throughout all subsequent visits, two-sided testing, and a significance level of 5%.  At visits 1 through 6 Placebo subjects were assigned a 56% chance of increasing by one level, 22% staying the same, and 22% decreasing by one frailty level, and Treated subjects were assigned a 33% chance of increasing by one level, a 33% chance of staying the same, and a 33% chance of decreasing by one frailty level relative to the previous visit. With these parameter values, at baseline 50% of subjects were at frailty level 0 and 50% at level 1 in each arm and at visit 6 the distributions for Placebo were 0: 25%, 1: 22%, 2: 20%, 3: 18%, 4: 11%, 5: 4% on the average across the 1000 simulations. Distributions for Treated were 0: 50%, 1: 24%, 2: 14%, 3: 11%, 4: 0%, 5: 0% on the average across the 1000 simulations.

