3.3.9. Blinding. This study is double blinded. Only the study pharmacist has knowledge of the medication each participant is taking. As per the requirement by the NIA-appointed DSMB, one study statistician has been and will remain unblinded. The unblinded study statistician will prepare DSMB reports as per the guidelines provided from the National Institute on Aging (<https://www.nia.nih.gov/research/dgcg/clinical-research-study-investigators-toolbox/data-and-safety-monitoring>). Any unblinded report will be reviewed during a closed DSMB session with only the unblinded statistician present and without any study investigators present.

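### The Aim 1 power simulation omits the planned placebo-to-metformin switch at diabetes conversion, so 86% overstates intention-to-treat power, all else equal; the blinding section also contradicts the unblinding at conversion

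*Combined protocol and SAP*

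**What the plan says.** **Switching.** Item 6, Study Procedures k) Management of conversions, has an oral glucose tolerance test confirm diabetes and a set of study measurements, including frailty, taken at that point. On disclosure it says: "After these repeat measurements are performed, the study allocation will be unblinded". Its rule for the placebo arm is that, "if receiving placebo, subjects will be initiated on metformin and titrated as above". An independent practitioner on the study staff then manages medication so that the PI stays blinded. Switching is expected: Pharmacological intervention (Item 6 i) schedules an extra plasma metformin level for placebo participants who start metformin.

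**Analysis.** The Overview states that "primary inference will be drawn based on intention to treat (ITT) analyses".

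**Power.** Section 3.D.3 sets the sample size ("With 60 completers per arm") and claims that "this study will achieve a power of 86% to detect an overall odds ratio of 0.20", based on "1000 simulated databases with 6 repeated measures per subject". For visits 1 to 6, "Placebo subjects were assigned a 56% chance of increasing by one level, 22% staying the same, and 22% decreasing by one frailty level"; treated participants have 33% for each step. In each arm 10% never leave their baseline level. Conversion and switching are not mentioned.

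**Treatment change elsewhere.** The Overview plans average complier and per-protocol analyses. Table 7 lists diabetes conversion and pioglitazone use as time-varying covariates. The text after Table 7 says that treatment changers will be described, and that principal stratification and marginal structural models will be considered.

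**Blinding.** Section 3.3.9 says: "Only the study pharmacist has knowledge of the medication each participant is taking". It then adds one unblinded statistician for the data and safety monitoring board.

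**The concern.** A placebo participant who converts starts the study drug and remains in the placebo arm for the primary analysis. Under the simulation's own premise of a metformin benefit, that person then moves towards the treated arm's course. The simulation gives every moving placebo participant the same step probabilities to the last visit, so the 86% describes a trial without the switch that this protocol requires. A reader using the figure to judge whether a null result is informative would be given too favourable a number.

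The blinding issue is separate. Allocation is disclosed during follow-up and frailty continues to be assessed afterwards. Exhaustion and physical activity, two of the five criteria, are self-reported. The plan protects the PI and is silent on anyone else who tests or scores frailty.

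**Working it through.** **1. Inputs.** From 3.D.3: 60 completers per arm; 6 measures; two-sided 5%; half of each arm at score 0 and half at score 1; 10% per arm fixed at baseline; placebo steps 56/22/22% (up/same/down); treated steps 33/33/33%. Scores are truncated at 0 and 5. The conversion rate is not given: the Background cites only a 31% relative reduction in diabetes onset. Cumulative placebo conversion by 24 months is therefore **assumed** at 10%, 20% or 30%, at a constant hazard per visit. Converters take new step probabilities from the next interval: the treated ones (full effect) or values halfway between the arms (half effect).

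**2. The plan's own figure, without switching.** A random-intercept cumulative-logit model, standing in for the plan's model, was fitted to simulated trials.
- Six measures as written (5 transitions): overall odds ratio 0.18, power 95.7% (300 runs). This does not reproduce 86%.
- Five measures (4 transitions): odds ratio 0.20, power 86.8% (400 runs). This is close to the stated pair.
- The stated visit 6 distributions do not follow from the stated steps. Five transitions give placebo 15/21/20/20/15/10% for scores 0 to 5, against the stated 25/22/20/18/11/4%.

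The code and random-effects structure are not given, so 86% is taken as the anchor and not called wrong.

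**3. Diluting 86%.** The standardised effect behind 86% power is 1.960 + 1.080 = 3.040. If switching shrinks the difference in slopes by a fraction f, then

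power = Φ(3.040 × (1 − f) − 1.960).

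Simulated slope differences (arbitrary units, 4 transitions) start from 2.288 without switching, and f = 1 − difference/2.288:

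| Assumed conversion | Full effect: difference, f | Power | Half effect: difference, f | Power |
|---|---|---|---|---|
| 10% | 2.185, 4.5% | Φ(0.943) = 83% | 2.235, 2.3% | Φ(1.010) = 84% |
| 20% | 2.078, 9.2% | Φ(0.801) = 79% | 2.181, 4.7% | Φ(0.938) = 83% |
| 30% | 1.960, 14.3% | Φ(0.644) = 74% | 2.121, 7.3% | Φ(0.858) = 80% |

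With 5 transitions and full effect, f is 4.7%, 9.7% and 15.1%, giving 83%, 78% and 73%.

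**4. Cross-check by refitting the model with switching, full effect, overall odds ratio test.**
- Variant near the stated figure: 86.8% falls to 84.0%, 81.8% and 79.0%, a loss of 2.8, 5.0 and 7.8 points.
- Literal inputs: 95.7% falls to 95.0%, 93.0% and 91.3%, a loss of 0.7, 2.7 and 4.4 points.

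Monte Carlo standard error is about 1 to 2 points. With no treatment effect, this model rejected in about 19% of trials in the 4-transition variant. The fitted powers are therefore a guide to direction and relative loss, not to absolute power.

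**5. Blinding, side by side.** Section 3.3.9 reserves knowledge of treatment to the pharmacist, plus the unblinded statistician. Management of conversions unblinds at conversion and gives medication to another member of the study staff. Both cannot be true. On who assesses frailty, the visit schedule places it within the history and physical examination. The screening section assigns that examination to a named geriatrician. The risk section has an investigator or trained staff accompany the walk, and a trained staff member or the PI conduct the interviews. None of these passages says that assessors other than the PI stay blinded.

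**The case against.** **The 86% is not shown to be too high in absolute terms.** This stands. The literal inputs give more than 86% even with 30% switching. A reader might infer that true power is below 80%, or that some other single figure is correct. The documents do not support that: the conversion rate is missing, the simulation code is not given, and the effect after switching is unknown because metformin is titrated stepwise.

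**Treatment change is already handled.** This stands in part. A reader might infer that data after conversion enter the analyses unmarked. They do not: diabetes conversion is a time-varying covariate in the adjusted analyses, and complier, per-protocol and other treatment-change analyses are planned or to be considered. None of them changes the power of the primary ITT comparison, which is what 3.D.3 reports.

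**Assessors may be blinded in practice.** This is possible. The named examiner may be the PI, whose blinding is protected; the name is removed, so this cannot be settled. The accompanied walk is described as a precaution against falls, not as scoring. A reader might infer that frailty is scored by staff who know the allocation; the documents do not say so. What remains is that the plan does not rule it out, and that the two sections conflict.

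**This is a pilot.** True, and the consequence is modest. A stated power should still describe the design that will be run.

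**Conclusion.** The point holds in a limited form. The protocol mandates a switch that the power simulation leaves out. If metformin reduces frailty as assumed, ITT power is lower than the same calculation with switching omitted. Anchored to 86%, the dilution gives about 83%, 79% and 74% with full effect, and 84%, 83% and 80% with half effect, at assumed conversion of 10%, 20% and 30%. Refitting the model gives smaller losses. At 10% conversion the loss is only about 1 to 3 points by any of these routes. The conclusion would fail if the placebo step probabilities were meant to be net of switching, but 3.D.3 does not say that.

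The contradiction between 3.3.9 and Management of conversions is plain on the text and needs no assumption. The gap in assessor blinding is an omission, not evidence of unblinded assessment.

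**What to change.** 1. Rerun the 3.D.3 simulation with conversion and switching, over a stated range of conversion rates and of effects after the switch, and restate the ITT power for each. ITT remains primary. The cost is a rerun of an existing simulation and a less favourable stated power.
2. Extend the blinding rule in Management of conversions from the PI to all staff who perform or score frailty assessments, and reconcile section 3.3.9 with it. The cost is wording and minor staffing logistics.

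An analysis using frailty data only up to the conversion assessment is optional. If added, it must be supplementary: conversion happens after randomisation and metformin is expected to affect it, so stopping there may remove different participants from each arm.

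No change to clinical management is proposed.
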